Final protocol: 2nd July 2004 Amendment 1: 15th October 2004 Amendment 2: 2nd December 2004 Amendment 3: 11th July 2005 Amendment 4: 10th August 2005 Amendment 5: 12th September 2006 CONFIDENTIAL

Page 21 of 51

(Amended 10 August, 2005)

Newborns recluted at birth: Neonatal blood will be collected from (i) heelprick and (ii) cord blood where possible, to measure the Het FBC, parasitemia (thick and thin blood smear), and baseline immunology, including levels of maternal antibodies to P. falciparum, and to carry out host and parasite genotyping. Collection of cord blood will allow us to obtain a larger sample volume for genetic and immunological testing, and for archiving purposes. Importantly, it will help us to clarify whether there has been in utero infection with P. falciparum, since actual exposure is more closely reflected from the cord than from the newborns' peripheral blood ([name], personal communication). The umbilical cord will be cleaned thoroughly with saline soaked gauze to wash off the blood on the surface and thus avoid contamination with maternal blood. Blood from fetal circulation in the cord will be collected from inside by venipuncture, using standard techniques. The possibility of materno-fetal transfusion caused by placental trauma at delivery, with its risks of congenital malaria, will be considered if the mother has proven parasitemia in her peripheral blood and/or placenta as documented by positive blood smears or histology, and accounted for in the analyses. In addition to the cord blood, 0.5-1 ml of peripheral blood will be drawn by heel prick within 24 hours of birth, and will serve as the core specimen at t=0 for immunological analysis. (Amended 11 July, 2005) (Amended 10 August, 2005)

Infants aged 0-2 months recruited after birth: Blood will be collected at 2,5 months of age from heel or fingerprick to measure the Hct, parasitaemia (thick and thin blood smear) and baseline immunology and to carry out host and parasite genotyping. (Amended 2 December, 2004) (Amended 11 July, 2005)

vii. Data Recorded

1. Clinical and parasitological data

a) Clinical malaria: Episodes of clinical malaria will be recorded from the information collected at weekly home visits or with cross-sampling at 5, 10, 12, 15, 20 and 25 2,5; 5,5; 10,5; 15 and 24 months if the child meets the case definition for malaria at that time, or if child presents to the health post with malaria. (Amended 2 December, 2004) (Amended 11 July, 2005)

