(Amended 11 July, 2005) (Amended 10 August, 2005)

viii. Outcome Variables

1. Clinical outcome variables

a) Primary clinical outcome variable

The experience of having at least one episode of clinical malaria in the second year of life *detected by passive case detection.* (Amended 2 December, 2004)

b) Secondary clinical outcome variables

1. Fever (axillary temperature \geq 37.5° C or a history of fever in the previous 24 hours)

2. Hct during first, second and subsequent malaria infections, and during the **24 months** cross-sectional surveys.

3. Density of parasitemia during first, second and subsequent malaria infections, and during the **24** *months* cross-sectional surveys.

4. Time to first clinical episode during the second year of life *detected by passive case detection*.

5. Number of clinical episodes during the first year of life *detected by active or passive case detection*.

6. Number of clinical episodes during the second year of life *detected by passive case detection*. (Amended 2 December, 2004)

2. Immunological outcome variables

a) Primary immunological outcome variables:

 Anti-*Pt*EMP1 antibodies in peripheral blood, as measured at 0, 5, 10, 12, 15, 20 and 25 2.5, 5.5,
10.5, 15 and 24 months of age. The outcome variable to be compared between the cohorts will be: -Antibody units converted from median fluorescence intensity [31]

2. Level-Magnitude and frequency of cytokines (IFN- γ , IL-10) in peripheral blood in response to *in vitro* stimulation with Pf parasite antigens, as measured at 0, 5, 10, 12, 15, 20 and 25 2.5, 5.5, 10.5, 15 and 24 months of age

3. Ratio of Th1 (IFN- γ , TNF α , IL-12 and IL-2) to Th2 (IL-10, IL-5, IL-4) cytokines in plasma, as measured at 0, 5, 10, 12, 15, 20 and 25 **2.5, 5.5, 10.5, 15 and 24** months of age.

4. Anti-GPI antibodies in peripheral blood as measured at 2.5, 5.5, 10.5, 15 and 24 months of age. The outcome variables to be compared between the cohorts will be: -Antibody units converted from ELISA titre -Antibody units converted from Functional Neutralization Assay.

Final protocol: 2nd July 2004 Amendment 1: 15th October 2004 Amendment 2: 2nd December 2004 Amendment 3: 11th July 2005 Amendment 4: 10th August 2005 Amendment 5: 12th September 2006 CONFIDENTIAL

Page 24 of 51

CSI/CISM

5. Host genetics:

-Presence of homozygote or heterozygote for each particular SNP. -Presence or absence of nominated haplotype for each gene.

(Amended 11 July, 2005) (Amended 10 August, 2005)

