Our prediction: We hypothesize that the level of antibodies will be statistically significantly lower in Cohort 2 as compared to either Cohort 1 or Cohort 3 at the 10 month old cross-samplings and that this reduction will correlate with an increased relative risk of one or more clinical episodes of malaria in the second year of life.

Proposed analysis: Immunological endpoints will be based upon levels of antibodies (intensity) and the ratio of Th1/Th2 cytokines at each of the cross-sectional time points. For the first analysis, values for antibodies and cytokine ratios for each cohort will be compared at each cross-sectional timepoint. For the second analysis, values for antibodies and cytokine ratios at each of the timepoints will be correlated with risk of clinical outcome(s) for each cohort and between cohorts. Immunological data will be analyzed in two different ways:

- **Cross-sectionally** the key analysis will be comparison of immunological markers between cohorts, not individuals, to show differences in the development of acquired immunity to malaria attributable to age of first exposure to Pf antigens. The key timepoint for comparison is considered to be 10 months. We will explore the profile of immune responses and how markers change with age. Specifically, we predict the following outcomes:

X1; t= 2,5 month 0 or enrollment. No difference between the 3 cohorts

X2, t=5 5,5 month: No difference between the 3 cohorts

X3, t=10 10,5 month (*key comparison*): Cohort 2 will have significantly lower levels of anti-PfEMP-1 antibodies and/or Th1/Th2 cytokine ratios than cohort 1 and 3. Cohort 1 = cohort 3. **X4**, t=12 month: same as X3.

X5- **X4**, t=15 month: same as X3.

X6, t= 20 month: No difference between the 3 cohorts.

X7- **X5**, t= 25 **24** month: same as X6. We expect the immune responses to equalize between cohorts by 20-25 months.

(Amended 2 December, 2004) (Amended 11 July, 2005)

- **Prospectively**: To look for correlates of immune responses and clinical outcome. Specifically, acquisition of immune response at the level of the individual subject (as opposed to cohort) in cohort 1 vs. 2, and correlation with how that individual responds to infection and the relative risk of clinical disease. We will evaluate whether lack of exposure at different ages (0-5 months, or 5-10 months) during first 2 years of life results in differences of antibody and/or cytokine markers between the different cohorts.

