-Antibody units converted from ELISA titre (titer log₂(titer/10)+1 with reference to last dilution causing positive ELISA as compared with non-specific background and the ratio of IgM, IgG1, IgG2, IgG3 + IgG4 isotypes as measured in the same way)

-Antibody units converted from Functional Neutralization Assay.

(Amended 11 July, 2005)

c) Analysis and interpretation of cellular immunoassays

- The **cytokine intracellular staining** of whole blood will provide information about Pf antigen specific expression of IFN- γ and IL-10 in peripheral blood, the phenotype of the lymphocyte population expressing each cytokine (produced by CD4 or CD8 T cells), as well as the status of activation (CD69 marker) of the cells. Data will be acquired by flow cytometry and analyzed using the CellQuestTM software. Results will be expressed as frequency (%) of cytokine positive CD4+ or CD8+ T cells, and mean fluorescence intensity. For statistical analysis, data on the mean frequency of cytokine expression will be compared between cohorts by t-test or regression analysis; p<0.05 will be considered statistically significant.

- The concentration of unknown cytokines (IFN- γ , IL-10, TNF- α , IL-5, IL-4 and IL-2 and IL-12) in plasma is calculated in the Cytometric Bead Array (CBA) or equivalent via extrapolation from a curve of known standards. Standard curves are plotted [cytokine calibrator concentration vs. FL-2 mean fluorescence intensity] using a 4-parameter logistic curve fitting model. Cytokine concentrations (pg/ml) are determined from these standard curves. If the plasma has a cytokine concentration below the detection limit for the assay, a value of 0 will be assigned. All data will be presented as mean \pm standard error. In addition, cytokine ratios will be calculated to determine the Th1 vs. Th2 balance of cytokines.

Final protocol: 2nd July 2004 Amendment 1: 15th October 2004 Amendment 2: 2nd December 2004 Amendment 3: 11th July 2005 Amendment 4: 10th August 2005 Amendment 5: 12th September 2006 CONFIDENTIAL

Page 35 of 51

Results will be analyzed using the manufacturer's software. Data will be analyzed by a general linear model analysis of variance (ANOVA) with pre-planned comparisons to generate two-tailored p-values. Fisher least significant-difference tests will be used to make appropriate post ANOVA comparisons.

d) Analysis and interpretation of immunogenetic data

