2. Reliance of caretakers for passive case detection. Prior to study start we will ask all parents/guardians of study participants to take their child to the health center whenever he/she feels unwell. During the previous *trials* vaccine trial conducted *by CISM* in Ilha Josina the mothers/guardians responded well and attended the health *facilities* facility frequently. (Amended 15 October, 2004)

Final protocol: 2nd July 2004 Amendment 1: 15th October 2004 Amendment 2: 2nd December 2004 Amendment 3: 11th July 2005 Amendment 4: 10th August 2005 Amendment 5: 12th September 2006 CONFIDENTIAL

Page 36 of 51

3. The volumes of blood which can be collected from newborn infants will limit the number and breadth of immunological assays which can be performed, but we have assigned priorities which we believe will allow us to meet our objectives. We anticipate that difficulties may be minimized by employing well-trained personnel experienced in working with newborns and infants.

4. We may not be able to adequately control for the effect of *in utero* exposure on T cell responses. We are collecting a medical history on the mother concerning previous births, and malaria infections. We are also collecting maternal blood, placental samples and cord blood in an attempt to gauge the extent of maternal infection at delivery. *Nevertheless these maternal factors should be equally distributed between the three cohorts, given that infants will be randomly allocated to these.* (Amended 2 December, 2004)

5. We do not know the specifics of decay of maternal antibodies in the population at Ilha Josina *Manhiça* and this could potentially confound our immunologic results. However, we are using data from Tanzania on the kinetics of maternal antibody decay in infants [49, 86] as a guide. Furthermore, the data obtained by CISM investigators indicates that there is a very low or non-existent incidence of clinical malaria episodes in infants less than 2 months in this area (see details included under Study Site), presumably due at least in part to the protective role of maternal antibodies, while the age-incidence of malaria episodes rises rather dramatically after 2 months of age; these data indicate that the presence of maternal antibodies after 2 months of age is not likely to be a major confounder in our proposed studies. (Amended 15 October, 2004)

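### The cohort comparisons of immune markers, with 10.5 months as key, name no adjustment for the 2.5-month value of the same marker, although that value is scheduled

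*Protocol*

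**What the plan says.** **The comparison.** Under Immunological data (D.xi.2.a), "values for antibodies and cytokine ratios for each cohort will be compared at each cross-sectional timepoint". On the cross-sectional part, "the key analysis will be comparison of immunological markers between cohorts, not individuals". The key time point is 10.5 months after amendment, and the section later describes the cross-sectional comparison as the primary immunological outcome. At the first sampling point it predicts no difference between cohorts.

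**The tests.** D.xi.2.c gives methods for the cellular assays only. For intracellular staining, "data on the mean frequency of cytokine expression will be compared between cohorts by t-test or regression analysis; p<0.05 will be considered statistically significant". For plasma cytokines, "Data will be analyzed by a general linear model analysis of variance (ANOVA) with pre-planned comparisons", followed by Fisher least significant difference tests. No covariate is named for either. D.xi.2.b defines the antibody outcomes and names no test.

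**The earlier measurement.** D.viii.2.a lists "Anti-GPI antibodies in peripheral blood as measured at 2.5, 5.5, 10.5, 15 and 24 months of age", and gives the same ages for anti-PfEMP1, antigen-stimulated cytokines and the Th1/Th2 ratio. D.vi schedules the 2.5-month draw, with immunological studies, for all infants. For infants recruited after birth, "Blood will be collected at 2,5 months of age from heel or fingerprick to measure the Hct, parasitaemia", and the same sentence adds baseline immunology. The first dose is also at 2.5 months (D.iii).

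**The concern.** Each infant's marker level at 2.5 months is to be measured, yet nothing in the stated analysis uses it when the cohorts are compared at 10.5 months. Two things follow if the two values are correlated. Variation between infants that existed before treatment stays in the error term. Any chance difference between cohorts at 2.5 months is also carried, in part, into the key contrast. Adjusting for a pre-treatment measurement of the same outcome targets the same cohort difference and removes both. The stake is the precision of the main immunological result; the type I error and the validity of the unadjusted comparison are not in question.

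**Working it through.** **1. The plan's own figure.** The only sample-size calculation is for the clinical primary outcome (D.ix): 78 per cohort, 80% power, rates 0.4 and 0.8 per person-year (relative risk 2), two-sided alpha 0.017. With n = (z_alpha + z_beta)² (r1 + r2)/(r1 − r2)²:

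(2.387 + 0.842)² × 1.2/0.16 = 78.2.

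This reproduces the stated 78, and 78/0.8 = 97.5 gives 98. It says nothing about the immune markers, for which the protocol states no standard deviation, effect size, power or correlation. I use 78 only as a plausible number per cohort. After the last amendment it would be nearer 350/3 × 0.8 = 93.

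**2. Unadjusted starting point.** D.xi.2.c uses p<0.05 for cytokines. The difference detectable with 80% power, in standard deviations (SD), is (1.960 + 0.842) × √(2/78) = 0.449 (0.411 at 93 per cohort).

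**3. Effect of adjustment.** With correlation rho between the 2.5- and 10.5-month values, the residual variance is (1 − rho²) times the raw variance. A contrast with 80% raw power then has power Φ(2.802/√(1 − rho²) − 1.960). The sample size cancels, so the result is the same at 78 and 93.

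| rho (assumed) | variance factor | power |
|---|---|---|
| 0.1 | 0.99 | 80.4% |
| 0.2 | 0.96 | 81.6% |
| 0.3 | 0.91 | 83.6% |
| 0.5 | 0.75 | 89.9% |

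**4. Chance imbalance.** With 78 per cohort, the baseline difference between two cohorts has a standard deviation of √(2/78) = 0.16 SD. The unadjusted contrast carries rho times that: 0.05 SD at rho 0.3 and 0.08 SD at 0.5. This is part of the usual standard error, not an addition to it.

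**5. Cost when rho is zero.** One slope is estimated for nothing. Variance rises by a factor of about 1 + 1/(3 × 78 − 5) = 1.0044, or 0.4%.

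**6. Missing 2.5-month values.** If a proportion m of infants lacks the baseline and is dropped, variance relative to the unadjusted analysis is (1 − rho²)/(1 − m):

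- m = 10%, rho = 0.1: 1.10
- m = 10%, rho = 0.3: 1.01
- m = 20%, rho = 0.3: 1.14
- m = 20%, rho = 0.5: 0.94

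Dropping infants can therefore lose more than adjustment gains. If missing baselines are filled with one overall mean, the factor is about 1 − (1 − m) rho². At m = 20% that is 0.99, 0.93 and 0.80 for rho 0.1, 0.3 and 0.5.

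**The case against.** **Covariates belong in the statistical analysis plan, and the stated methods could take one.** Regression and a general linear model both accept a baseline term, and the D.xi.2.a sentence says what is compared and when, not how. This stands to the extent that the protocol does not forbid adjustment. It does name tests for the cytokines, however, and one of them, the t-test, cannot carry a covariate. Naming the adjusted model would also settle the open choice between t-test and regression.

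**No antibody test is stated.** Correct. For anti-PfEMP1 and anti-GPI the document fixes only the time-point-by-time-point comparison, so a reader who infers that an unadjusted antibody test has been chosen goes beyond the text.

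**The gain may be negligible.** This stands. The correlation is undocumented. The protocol reports essentially no malaria in the first two months and attributes this to maternal antibody. Antibody at 2.5 months may therefore be largely maternal, while antibody at 10.5 months reflects the infant's own exposure. Nothing in the document shows that cytokines correlate more strongly.

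**Maternal antibody as confounder.** A reader might infer that the plan admits a confounder and leaves it uncontrolled, since D.xii item 5 says of maternal antibody decay that "this could potentially confound our immunologic results". The same item concludes that after 2 months it is unlikely to be a major one. Because cohorts are allocated at random, it cannot systematically bias the contrast. What is left is variance and chance imbalance.

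**Is 2.5 months truly pre-dose?** Sample and first dose share a nominal age, and the order is not stated. The predicted absence of a cohort difference and the baseline label suggest that blood comes first, but this needs confirming.

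**Conclusion.** The point holds as an optional gain in efficiency. The stated cohort comparisons and cytokine tests name no baseline covariate, the same markers are scheduled at an age the plan treats as baseline, and adjusting for that value is at worst nearly neutral if no infant is dropped. The gain in power from 80% is under 1 point at rho 0.1, about 4 points at 0.3 and about 10 at 0.5. These figures rest on an assumed correlation, a linear relation on the analysis scale, and a 2.5-month sample taken before the first dose.

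Two stronger readings are not supported. Adjustment is not cost-free: blood volume limits the assays (D.xii item 3), so baselines may be missing, and a complete-case model can do worse than no adjustment. Nor does the criticism extend to haematocrit at 24 months. D.xi.1.a specifies a logistic analysis of haematocrit below 25%, similar to the multivariable model for clinical malaria, and the protocol states no unadjusted model for the 24-month value.

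**What to change.** In D.xi.2.a and D.xi.2.c, state that each marker at 5.5, 10.5, 15 and 24 months is compared between cohorts by a linear model (ANCOVA) with cohort and the 2.5-month value of the same marker, 10.5 months remaining key. Add the following:

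- Confirm that the 2.5-month blood is drawn before the first dose. Do not use the 5.5-month value as a covariate, since Cohort 1 has been treated by then.
- Keep infants with no 2.5-month value, by one overall mean (not cohort means) or a missing indicator.
- Choose a transformation that copes with plasma cytokines set to 0 below the detection limit, with a rule for ratios whose denominator is 0.
- Leave titres already on the log2 scale as they are.

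The cost is one degree of freedom per model, or two with a missing indicator. No new samples, visits or assays are needed.

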A follow-up study, performed at the same site in Ifakara, Tanzania, addressed the question of whether intermittent prophylaxis (IPTi), as opposed to continuous prophylaxis, might maintain the benefits during the first year of life without engendering a rebound effect during the second year [2]. This study, conducted in 701 infants, showed that intermittent prophylaxis with SP at 2, 3 and 9 months of age (with suppression of parasitemia presumably lasting for approximately one month after administration of each SP dose [5]) was also effective in reducing the frequency of episodes of severe anemia (0.06 vs. 0.11 episodes per person-year at risk; protective efficacy 50% [95% CI 8-73]) and of clinical malaria (0.15 vs. 0.36 episodes per person-years at risk; protective efficacy 59% [95% CI 41-71]) in the first year of life, compared with administration of placebo. However, in contrast to the first study, there was no evidence of a rebound effect with regard to clinical malaria or anemia during the second year of life in the group who received the intermittent prophylaxis as compared to those who received placebo.

During the extended follow-up of the participants in this trial (Schellenberg et al, submitted for publication), who were followed up to age 24 months, IPTi produced a sustained reduction in the risk of clinical malaria during the second year of life, with a protective efficacy of 35.7% (95% CI 12, 52). These results show there is a sustained reduction in the risk of clinical malaria in children receiving IPTi extending well beyond the duration of the pharmacological effects of SP.

Surveillance methods in both studies were similar, both drug regimens appeared highly effective in compliant study subjects, and levels of drug-resistance are low in Ifakara. Therefore, data suggest that infants receiving intermittent prophylaxis, but not those on continuous prophylaxis up to 48 weeks

Final protocol: 2nd July 2004 Amendment 1: 15th October 2004 Amendment 2: 2nd December 2004 Amendment 3: 11th July 2005 Amendment 4: 10th August 2005 Amendment 5: 12th September 2006 CONFIDENTIAL

Page 3 of 51

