Anti-disease Antibody responses - Anti-hemozoin and anti-GPI antibodies: The temporal correlation between schizont rupture and acute febrile episodes, with sharp increase in the concentration of circulating cytokines, is consistent with the view that parasite products released from infected erythrocytes at the time of schizogony may trigger the inflammatory cytokine cascade, leading to the onset of symptoms. Soluble parasite products or "toxins" can activate macrophages to release TNF- α , IL-1 and IL-6, and may directly activate the vascular endothelium and upregulate expression of adhesins such as intercellular adhesion molecule 1 (ICAM-1) and VCAM-1 [91], which can mediate parasite cytoadherence, thereby contributing to organ-specific and cerebral disease syndromes [97]. Furthermore, both cytokines and malarial toxins can each directly induce the expression of other pro-inflammatory loci such as that for inducible nitric oxide synthase (iNOS), thereby raising levels of nitric oxide(NO), which may be a regulator of pathogenesis. There is growing evidence sustaining the idea that antibodies to TNF- α -stimulating malaria toxins may explain the phenomenon of clinical tolerance in malaria, and it may be possible to develop an anti-disease vaccine based on modified forms of these toxins. We propose to measure acquired immune responses to hemozoin andGPI, two candidate malaria toxinsthat are thought to contribute to the development of disease and to be targets of clinical immunity [90-97]. The malarial pigment (haemozoin) may be a factor in the production of the malarial paroxysm, and may have a role in the pathogenesis of malaria anemia by decreasing red blood cell deformability through oxidative damage of infected erythrocytes, and by inhibiting erythropoiesis. Immunization against chemically synthetic parasite GPI confers protection against cerebral pathology, acidosis, and pulmonary edema in the best available small animal model of severe and fatal pathogenesis [97]. Lacking memory responses, anti-GPI antibodies may decay rapidly and thus be particularly exposuredependent, and thus be especially sensitive to the interventions we propose. However, the relationship of anti-hemozoin and anti-GPI immunity to pathogenesis and clinical immunity in human malaria has not been adequately investigated. (Amended 11 July, 2005)

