of life, presumably due to protection afforded by maternal antibodies. Following 2 months, the agespecific incidence of clinical episodes of malaria increases to levels near that of the second year of life (see Section D, Study Site). Thus cohort 1 should be essentially free of parasitemia during the first 5 months of age, cohort 2 will be exposed to Pf parasites until 5 months of age, and then not exposed until approximately 10 months and cohort 3 will have continuous exposure. Since SP and AS does not affect pre-erythrocytic stage exposure, all children will have pre-erythrocytic stage exposure continuously. Therefore, it is the degree of exposure to erythrocytic stage antigens that is the independent variable manipulated by the intervention. We have chosen to administer the chemoprohylaxis at 2,5 – 10,5 months and not at 2-10 months of age to avoid possible interactions between the SP+AS treatment and the responses to the EPI vaccines. The SP+AS treatment will be administered 15 days prior to the EPI vaccines (which are administered at 0, 2, 3, 4 and 9 months of age), a sufficient time lag to avoid such interactions. (Amended 15 October, 2004) (Amended 2 December, 2004) (Amended 10 August, 2005)

For our primary outcome variable, we will compare the risk of having at least one malaria episode **as detected by passive case detection** between 12-24 months in the three cohorts. We have chosen our primary outcome variable and follow-up period (12-24 months) in order to duplicate the parameters from the two previous clinical trials upon which this study is based [1, 2]. We anticipate that Cohort 2, with exposure to blood stage antigens blocked during the latter half of infancy, will have a statistically significantly higher risk of at least one episode of malaria between 12-24 months of age than will Cohorts 1 and 3, and that by the same measure, Cohorts 1 and 3 will be similar to each other in terms of risk. Because we are aware that an affect on clinical outcome could be seen even after year two, we will also include follow-up during year three consisting of home visits every 3 months. Children will continue to have full access to both the llha Josina **Maragra** Health Center and Manhiça Hospital for care. In addition, children will be followed long-term for mortality through the demographic surveillance system (DSS) already in place. **(Amended 15 October, 2004) (Amended 2 December, 2004)**

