If the pregnant woman/mother is HIV-positive she will not be invited to participate in the study, and will be followed up at the Day Hospital following standard procedures, according to national guidelines, which includes HAART (see above for details). The investigators will not have access to any of the VCT center records and will receive no information at all on the HIV-status of women who are not enrolled in the study.

(Amended 15 October, 2004) (Amended 2 December, 2004) (Amended 11 July, 2005) (Amended 10 August, 2005)

iii. Experimental Cohorts

Infants who meet the criteria to participate in the study will be assigned to one of the 3 cohorts by block randomization, in order to adjust for seasonality of malaria infection. Thus, for every 6 infants, 2 will be randomized to each of the 3 cohorts. Enrollment of infants will continue over a one year period. Cohort 1 will receive chemoprophylaxis with SP+AS from 2 to 5 2,5 to 5,5 months of age (doses at months 2, 3 & 4 2,5; 3,5; 4,5) and placebo from 5 to 10 5,5 to 10,5 months of age. Cohort 2 will receive placebo from 2 to 5 2,5 to 5,5 months of age and chemoprophylaxis from 5-10 5,5 to 10,5 months of age (doses at months 5, 6, 7, 8 & 9 5,5; 6,5; 7,5; 8,5; 9,5), and Cohort 3 will receive placebo from 2 to 10 2,5 to 10,5 months of age. Placebo tablets will look exactly the same as the SP and AS tablets, with the same shape, size and colour. The treatment or placebo will be packed in individually numbered envelopes/bags. Doses of SP+AS/placebo will be administered on a monthly basis by a health assistant according to bodyweight (SP: single dose of 25 mg/kg Sulphadoxine and 1.25 mg/kg Pyrimethamine; AS: 4 mg/kg/day for three days). Tablets will be crushed and mixed with water on a tablespoon and administration will be directly observed. Infants will be observed for 30 minutes and a repeat dose will be given if vomiting occurs within that time. Infants from all three cohorts will be invited to the health post on month 2, 3, 4 and 9 to receive the EPI vaccines and the investigators will make sure they receive them. Subjects will be followed by active case detection as well as passive case detection until 10.5 months of age and by passive case detection and montly home visits from 10,5 to 25 24 months of age (see section v). (Amended 2 December, 2004) (Amended 11 July, 2005)

Rationale for the 3 cohorts:

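### The key 10.5-month immunology comparison cannot show an effect of age of first exposure, because it does not separate age window from recency and duration of exposure

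*Protocol*

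**What the plan says.** Section D.iii gives the schedule, with struck-out and amended ages run together. For Cohort 1 it reads "doses at months 2, 3 & 4 2,5; 3,5; 4,5) and placebo from 5 to 10 5,5 to 10,5 months of age". For Cohort 2 it reads "chemoprophylaxis from 5-10 5,5 to 10,5 months of age (doses at months 5, 6, 7, 8 & 9 5,5; 6,5; 7,5; 8,5; 9,5". Cohort 3 takes placebo throughout. Section C describes the intended result for Cohort 2: "cohort 2 will be exposed to Pf parasites until 5 months of age, and then not exposed until approximately 10 months".

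Section D.xi.2.a calls the between-cohort cross-sectional comparison the key immunology analysis and gives its purpose as "to show differences in the development of acquired immunity to malaria attributable to age of first exposure to Pf antigens". It adds: "The key timepoint for comparison is considered to be 10 months". The amended list of predictions places that key comparison at 10.5 months and expects that "Cohort 2 will have significantly lower levels of anti-PfEMP-1 antibodies and/or Th1/Th2 cytokine ratios than cohort 1 and 3. Cohort 1 = cohort 3". The same pattern is predicted at 15 months, no difference is predicted at 5.5 months, and the cohorts are expected to equalise by 20 to 25 months. The section treats the cross-sectional comparison as the primary immunological outcome. Section D.xi.2.e repeats the attribution to age of first exposure for the oxidative stress markers.

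Two background statements in section A matter here. One concerns the duration of cover per SP dose: "with suppression of parasitemia presumably lasting for approximately one month after administration of each SP dose". The other concerns one of the outcomes listed as primary in section D.viii.2: "anti-GPI antibodies may decay rapidly and thus be particularly exposuredependent".

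**The concern.** The plan names one cause, age of first exposure, for a contrast in which that factor does not vary as the predictions require. At the chosen sampling time the cohorts also differ in how recently, and for how long in total, they could have met the parasite.

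Suppose Cohort 2 is lower at 10.5 months. The plan's wording would let this be reported as evidence that early exposure fails to build immunity. It could also be offered as the immune explanation of any clinical difference, because the plan expects the reduction to correlate with malaria risk in the second year. The same ordering could arise to some degree if infants responded equally well at every age and Cohort 2 had simply met no antigen lately.

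**Working it through.** **Inputs.** Active doses are at 2.5, 3.5 and 4.5 months (Cohort 1) and at 5.5, 6.5, 7.5, 8.5 and 9.5 months (Cohort 2), from section D.iii. Cover per dose is d, about 1 month (section A, stated for SP). As an assumption, d is also varied from 0.75 to 1.5 months. Samples are at 5.5, 10.5 and 15 months (section D.vi).

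**Step 1: the plan's own end of cover.** End of cover = age at last dose + d. For Cohort 2 this is 9.5 + 1 = 10.5 months, which matches the stated end of chemoprophylaxis and is also the age at the key sample. For Cohort 1 it is 4.5 + 1 = 5.5 months.

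**Step 2: uncovered time (d = 1).** Uncovered months since age 2.5 = (age at sample − 2.5) − months of cover.

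| Sample | Quantity (months) | Cohort 1 | Cohort 2 | Cohort 3 |
|---|---|---|---|---|
| 5.5 months | Uncovered since 2.5 | 3 − 3 = 0 | 3 − 0 = 3 | 3 |
| 10.5 months | Uncovered since 2.5 | 8 − 3 = 5 | 8 − 5 = 3 | 8 |
| 10.5 months | Uncovered in the last 5 | 5 | 0 | 5 |
| 10.5 months | Time since cover ended | 10.5 − 5.5 = 5 | 10.5 − 10.5 = 0 | never covered |
| 15 months | Uncovered since 2.5 | 12.5 − 3 = 9.5 | 12.5 − 5 = 7.5 | 12.5 |
| 15 months | Uncovered in the last 3 | 3 | 3 | 3 |
| 15 months | Time since cover ended | 15 − 5.5 = 9.5 | 15 − 10.5 = 4.5 | never covered |

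At 10.5 months Cohort 2 is lowest on recent exposure and also on total uncovered time, and it alone lacked exposure in the later window. All three differences point the same way.

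**Step 3: sensitivity to d.** With d from 0.75 to 1.5, Cohort 2's cover ends at 10.25 to 11.0 months. Its uncovered time in the last 3 months is at most 3 × (1 − 0.75) = 0.75 months, against 3.0 in Cohorts 1 and 3. The conclusion does not depend on d being exactly 1.

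**Step 4: age at which exposure first becomes possible (from 2.5 months).** Cohort 2: 2.5. Cohort 3: 2.5. Cohort 1: 5.5 with d = 1 (3.25 with d = 0.75; 6.0 with d = 1.5).

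| Pair | Designed age of first exposure | Prediction at 10.5 months |
|---|---|---|
| Cohort 2 vs Cohort 3 | same | differ |
| Cohort 1 vs Cohort 3 | different | equal |

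The predictions run opposite to the stated attribution. They fit a contrast of exposure windows, which is not the same thing as age of first exposure.

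**The case against.** The strongest reply is that this is a loose phrase and that the plan already holds the means of dealing with recency. Much of that is fair:

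- The prospective paragraph of the same section, and the aims in section C, describe the contrast correctly as exposure in one age window or the other.
- A 15-month sample is planned, with the same prediction.
- Cohort 1 is in the mirror position at 5.5 months, with cover just ending.
- Convalescent samples one month after a first episode fix the time since infection.
- With the 12-month sample removed, 10.5 months is the last sample before the 12 to 24 month outcome window, so it is a sensible prospective correlate.

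None of these is the key comparison, and none changes the stated attribution. The episode-count covariate in section D.iii does not settle recency either. It is a count, and weekly smears are taken only with fever or a history of fever.

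It can also be said that realised first infection may come later in Cohort 2 than in Cohort 3, because an infant not infected by 5.5 months is then protected. At 10.5 months, however, such infants have had little or no exposure at all. They inform a comparison of exposed with unexposed infants, not of early with late first exposure.

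Three stronger readings should be resisted:

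- **That lower antibodies in Cohort 2 do reflect absent antigen.** The documents do not show this. The rapid-decay remark says only that anti-GPI antibodies may behave so, and it ties this to their lack of memory responses. The 10.5-month prediction names anti-PfEMP-1 antibodies and cytokine ratios.
- **That the deficit can be sized from an antibody half-life.** No half-life is given. The fraction left after 5 antigen-free months, 0.5^(5/h), is 3% for an assumed h of 1 month and 75% for an assumed 12 months. It is also a fall within Cohort 2, not a difference from Cohorts 1 or 3.
- **That Cohort 3 minus Cohort 1 at 5.5 months, set against Cohort 3 minus Cohort 2 at 10.5 months, would give a clean age contrast.** It compares 3 months of suppression with 5. On the Manhiça rates in section D.i, clinical episodes removed are about 13 weeks × 0.4/100 = 0.05 against 22 weeks × 0.7 to 0.9/100 = 0.15 to 0.20. That is roughly three to four times as many, and it favours the hypothesis.

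**Conclusion.** The attribution to age of first exposure is wrong for this design and should be corrected. At 10.5 months recency, total duration and age window of exposure are confounded: 0 uncovered months of the last 5 in Cohort 2 against 5 in each of the others, with about one month of cover per dose. Absence of recent exposure would be expected to contribute to the predicted pattern. How much it contributes cannot be determined from the documents, and no size for the between-cohort deficit is offered here.

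The conclusion rests on the stated dosing ages and the protocol's suppression time, and it survives cover of 0.75 to 1.5 months per dose. It concerns the primary immunological comparison, which serves a secondary aim. A reader might infer that the trial's main conclusion is also compromised. That does not follow, because the primary clinical outcome in the second year of life is not touched by this point.

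**What to change.** 1. In sections D.xi.2.a and D.xi.2.e, replace age of first exposure with exposure during the 2.5 to 5.5 or the 5.5 to 10.5 month window.
2. State that a Cohort 2 deficit at 10.5 months may reflect lack of recent exposure and does not by itself show impaired acquisition of immunity.
3. Keep 10.5 months as the correlate measured before the outcome window. Require the deficit to persist in the planned 15-month sample before calling it impaired acquisition. By then every cohort is at least 4.5 months past cover (4.0 to 4.75 months for Cohort 2 over the range of d above). Note that this sample lies inside the 12 to 24 month window, so outcome episodes can influence it, and that time off cover and total uncovered time still differ between cohorts.
4. Use the 5.5-month Cohort 1 versus Cohort 3 comparison and the convalescent samples as supportive evidence on recency only, not as a new key contrast. The convalescent samples cover only infants who have an episode.

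The cost is wording in the immunology plan. No visits, samples or assays are added, and the 10.5-month result taken alone supports a weaker claim.
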